## 1 Introduction

### 1.1 Background

Coronaviruses are single stranded ribonucleic acid viruses, capable of causing life threatening disease in humans and animals. The novel severe acute respiratory syndrome coronavirus 2 (SARS-CoV-2) was initially identified during an outbreak of atypical viral pneumonia cases of unknown cause in the People's Republic of China (hereafter "China") in December 2019. Most of the initial infections outside of China were travel associated (i.e., from people who had travelled from the infected regions of China to other countries), although person to person transmission in other countries was quickly established. The disease caused by SARS-CoV-2 has been designated as coronavirus disease 2019, known as COVID-19 ([World Health Organization \[WHO\] disease outbreak news, 2020](#)).

Most people with SARS-CoV-2 infection develop only mild (40%) or moderate (40%) disease. However, approximately 15% develop severe disease that requires oxygen support, and 5% have critical disease with complications such as respiratory failure, acute respiratory distress syndrome, sepsis and septic shock, thromboembolism, and/or multiorgan failure, including acute kidney injury and cardiac injury. Older age, smoking and underlying noncommunicable diseases, such as diabetes, hypertension, cardiac disease, chronic lung disease, and cancer have been reported as risk factors for severe disease and death.

Severe acute respiratory syndrome coronavirus 2 infection is also associated with mental and neurological manifestations, including delirium or encephalopathy, agitation, ischemic and hemorrhagic stroke, meningoencephalitis, impaired sense of smell or taste, anxiety, depression, and sleep problems. In many cases, neurological manifestations have been reported even without respiratory symptoms. Case reports of Guillain-Barré syndrome and meningoencephalitis among people with SARS-CoV-2 infection have also been reported. Clinical manifestations of SARS-CoV-2 infection are generally milder in children compared with adults. Relatively few cases of infants confirmed with SARS-CoV-2 infection have been reported. However, most recently a multisystem inflammatory syndrome temporally associated with SARS-CoV-2 infection in children and adolescents has been described ([WHO Guidelines, 2020](#)).

Coronavirus entry into host cells is an important determinant of viral infectivity and pathogenesis. It is also a major target for host immune surveillance and human intervention strategies. It has been established that SARS-CoV-2 binds via the angiotensin-converting enzyme 2 (ACE2) receptor located on epithelial and endothelial cells which traverse multiple

organs ([Varga et al., 2020](#)). SARS-CoV-2 infection is initiated by binding of the SARS-CoV-2 spike protein to ACE2 via the receptor binding protein (RBD) of the spike protein, which mediates viral entry into the target cells. The virus is mutating, indicating that virulence and transmission will shift over time, and showing diversity in this critical surface protein. New evidence suggests there are 2 strains of SARS-CoV-2; L-type and S-type ([Tang et al., 2020](#)). S-type is the less aggressive (30%); the L-type is now the most prevalent strain (70%) and is more aggressive. Additionally, individuals appear to be affected to different degrees with varying symptoms and outcomes. These findings strongly support an urgent need for immediate comprehensive studies and robust validation of testing methods that combine genomic data, chart records and clinical symptoms, to help better understand the disease, enable risk assessment, triage and support public health resource planning.

## 1.2 CT-P59

CT-P59 is a monoclonal antibody targeted against SARS-CoV-2 spike RBD as a treatment for SARS-CoV-2 infection. The dosage form of CT-P59 is solution concentrate for dilution for administration in a single intravenous (IV) infusion.

The main mechanism of action is binding to SARS-CoV-2 RBD and the cellular receptor, ACE2, thus blocking the SARS-CoV-2 infection. Although it is known that in many virus infections antibodies can remove the virus-infected cells via antibody Fc-dependent function such as antibody dependent cellular cytotoxicity, it's unlikely that CT-P59 induces antibody Fc-dependent virus clearance, considering the life cycle of SARS-CoV-2 which is assembled inside cells and released via exocytosis. However, it is postulated that there are additional mechanisms of CT-P59 mediated virus clearance by opsonization and complement activation (i.e., antibody dependent, complement-dependent virolysis or antibody dependent phagocytosis).

### 1.2.1 Nonclinical Studies

The nonclinical program for CT-P59 has been designed to support clinical studies. Detailed information regarding the nonclinical pharmacology and toxicology of CT-P59 can be found in the Investigator's brochure (IB).

### 1.2.2 Clinical Studies

CT-P59 has not been administered in humans yet.

## 1.3 Study Rationale

There are currently no approved monoclonal antibody therapies available to treat coronaviruses such as SARS-CoV-2 and there is an urgent public health need for the rapid development of such interventions. On 11 March 2020, the WHO declared the SARS-CoV-2 infection outbreak a global pandemic as there were more than 118,000 cases in 114 countries, and 4,291 people had lost their lives. According to the [WHO coronavirus disease situation report-135](#), about 6.28 million people were confirmed to have SARS-CoV-2 infection in 216 countries and fatalities exceeded about 380,000.

CT-P59 is currently being developed by the Sponsor as a potential treatment for SARS-CoV-2 infection. The anticipated high affinity and targeted effect of CT-P59 is expected to enable antiviral activity. In this study, safety, tolerability, and virology of CT-P59 will be evaluated in patients with mild symptoms of SARS-CoV-2 infection.

### 1.3.1 Rationale for Study Population

The study population depend on the clinical data and recommendation from the regulatory authority and CELLTRION's development program is focusing on evaluating safety and tolerability in patients with mild symptoms of SARS-CoV-2 infection. The expected patient population is adults only.

### 1.3.2 Rationale for Dose Selection

In this study, there will be three dose levels and an approximate 2-fold increase between doses. The planned starting dose is 20 mg/kg and the proposed top dose is 80 mg/kg.

The pharmacokinetic (PK) profile of CT-P59 is expected to be similar to those of CT-P27, an anti-influenza antibody drug to treat influenza under development by the Sponsor. CT-P27 drug product is a combination of the two human immunoglobulin G1 monoclonal antibodies. This is due to the structural similarity between the CT-P27 monoclonal antibodies and the CT-P59 monoclonal antibody, in that CT-P59 shares an identical human immunoglobulin G1 Fc region backbone with the two monoclonal antibodies of CT-P27.

Doses of CT-P27 in the range of 7.5 to 30 mg/kg were shown to exhibit increasing efficacy in virus-challenged mice and ferrets and are also within the range of doses for other approved human monoclonal antibodies for IV infusion.

The efficacious dose of CT-P59 in ferrets was determined as 30 mg/kg based on viral load and pathology. The nonhuman primate efficacious doses estimated as partial areas under the concentration-time curve (AUCs) ( $AUC_{0-24hr}$ ,  $AUC_{0-48hr}$ ,  $AUC_{0-72hr}$ ) equivalent to the ferret

partial AUCs at 30 mg/kg were about 12-18 mg/kg. Taking the assumption of no PK difference (partial AUCs) between human and nonhuman primates as well as the similar PK assumed between CT-P27 and CT-P59 into account, 20 mg/kg of CT-P59 will be likely to be efficacious in patients as well. Thus, the starting dose of 20 mg/kg of CT-P59 was selected as an effective dose for clinical trials of CT-P59.

In the 2-week repeat dose nonhuman primate toxicity study of CT-P27, the no-observable-adverse effect-level was 320 mg/kg. Applying a safety factor of 10, it was expected that a dose of up to 32 mg/kg could be supported as posing a very low risk of inducing adverse effects in human. In clinical trials, doses up to 90 mg/kg of CT-P27 were well tolerated. As 400 mg/kg of top dose is selected for 2-week repeat dose toxicology of CT-P59, greater safety factor over that of CT-P27 is expected to support the clinical trials.

The half-lives of the components of CT-P22 and CT-P23, comprising CT-P27, are approximately 17 days and 18 days, respectively. Assuming that the PK of CT-P59 and CT-P27 will be similar, due to the structural similarity between the CT-P27 and the CT-P59, in that an identical human immunoglobulin G1 Fc region backbone, the expected half-life of CT-P59 is 18 days in human.

The further nonclinical results of CT-P59 will be updated in the IB and will serve as the rationale behind dose selection. Safety data from cohort 1 and 2 (10 mg/kg, 20 mg/kg respectively) up to Day 7 in Study CT-P59 1.1 to be conducted in healthy subjects will be submitted for the regulatory's review prior to the dosing of this study, Study CT-P59 1.2, in addition to the nonclinical data. The Data and Safety Monitoring Board (DSMB) members of the healthy and the mild patient studies (Studies CT-P59 1.1 and CT-P59 1.2, respectively) will consist of the same members and the DSMB will be required not to proceed with the dosing of the next cohort in the patient study if there is any safety concern raised in the dose already evaluated in healthy subjects.

CT-P59 will be administrated intravenously. Several human antibodies are approved for IV infusion, which is the same route of administration of CT-P59.

## **1.4 Benefit and Risk Assessment**

Despite the fact that numerous entities are under investigation, no potent and highly targeted antiviral options are available for treatment and/or prophylaxis of coronaviruses such as SARS-CoV-2 at present.

CT-P59 has not been administered in humans yet, and therefore, the benefits or risks in humans are unknown at this time.

There may not be benefits for an individual patient, there may be benefits to society if a safe, efficacious therapeutic agent can be identified during this global SARS-CoV-2 infection outbreak.

The same global independent DSMB will ensure continued review of emerging data for both Studies CT-P59 1.1 and CT-P59 1.2.

More detailed information about the known and expected benefits and risks and reasonably expected adverse events (AEs) of CT-P59 may be found in the current version of the IB.

The Sponsor will immediately notify the Principal Investigator if any additional safety or toxicology information becomes available during the study.

This study will be performed in compliance with the protocol, International Council for Harmonisation (ICH) Good Clinical Practice (GCP) and applicable regulatory requirements. Aspects of the study concerned with the investigational medicinal product(s) will meet the requirements of European Union – Good Manufacturing Practice.

The Sponsor and Investigator may take appropriate urgent safety measures in order to protect the patients of a clinical study against any immediate hazard to their health or safety. If such measures are taken, the Sponsor shall immediately give written notice to the licensing authority and the relevant ethics committee of the measures taken and the circumstances giving rise to those measures.

## **2 Study Objectives and Endpoints**

### **2.1 Study Objectives**

#### **2.1.1 Primary Objective**

- To evaluate the preliminary safety and tolerability of CT-P59 up to Day 14 of the last enrolled patient

#### **2.1.2 Secondary Objectives**

- To evaluate the viral efficacy and characterization of SARS-CoV-2 viral isolates
- To evaluate the efficacy of CT-P59
- To evaluate the PK of CT-P59
- To evaluate additional safety of CT-P59 including immunogenicity

## **2.2 Study Endpoints**

### **2.2.1 Primary Endpoints**

Primary endpoints will be analyzed based on the data up to Day 14 of the last enrolled patient.

- Treatment-emergent adverse events (TEAEs)
- Treatment-emergent serious AEs (TESAEs)
- Treatment-emergent AEs of special interest (TEAESI; infusion related reactions including hypersensitivity/anaphylactic reaction)
- Potential effects on the incidence of antibody-dependent enhancement (ADE)
- Vital signs (blood pressure, heart rate, body temperature, SpO2 and respiratory rate)
- Hypersensitivity monitoring
- Twelve-lead electrocardiogram (ECG)
- Severe Acute Respiratory Syndrome Coronavirus infection related signs and symptoms
- Radiography (chest x-ray and/or chest CT)
- Clinical laboratory test (clinical chemistry, hematology, and urinalysis)

## **2.2.2 Secondary Endpoints**

Secondary virology, efficacy, PK, and safety endpoints will be analyzed.

### **2.2.2.1 Virology**

- Viral shedding in nasopharyngeal swab specimens based on quantitative polymerase chain reaction (qPCR) and cell culture
- Genotyping of SARS-CoV-2 viral isolates

### **2.2.2.2 Efficacy**

- Time to clinical recovery up to Day 28
- Proportion of patients with clinical recovery up to Day 7, 14, 28
- Proportion of patients requiring supplemental oxygen up to Day 7, 14, 28
- Proportion of patients with intensive care unit transfer up to Day 7, 14, 28
- Proportion of mechanical ventilation up to Day 7, 14, 28
- Proportion of patients with all-cause mortality up to Day 14, 28
- Proportion of patients with hospital admission up to Day 14, 28

### **2.2.2.3 Pharmacokinetics**

- Area under the concentration-time curve from time zero to infinity ( $AUC_{0-\infty}$ )
- Dose normalized  $AUC_{0-\infty}$  ( $AUC_{0-\infty}/\text{Dose}$ )
- Area under the concentration-time curve from time zero to the last quantifiable concentration ( $AUC_{0-\text{last}}$ )
- Dose normalized  $AUC_{0-\text{last}}$  ( $AUC_{0-\text{last}}/\text{Dose}$ )
- Maximum serum concentration ( $C_{\max}$ )
- Dose normalized  $C_{\max}$  ( $C_{\max}/\text{Dose}$ )
- Time to  $C_{\max}$  ( $T_{\max}$ )
- Terminal half-life ( $t_{1/2}$ )

- Percentage of  $AUC_{0-\infty}$  obtained by extrapolation (% $AUC_{ext}$ )
- Terminal elimination rate constant ( $\lambda_z$ )
- Total body clearance (CL)
- Volume of distribution during the elimination phase ( $V_z$ )

#### **2.2.2.4 Safety**

- Treatment-emergent adverse events (TEAEs)
- Treatment-emergent serious AEs (TESAEs)
- Treatment-emergent AEs of special interest (TEAESI; infusion related reactions including hypersensitivity/anaphylactic reaction)
- Potential effects on the incidence of ADE
- Incidence of anti-drug antibodies (ADAs) and neutralizing antibodies (NAbs)
- Vital signs (blood pressure, heart rate, body temperature,  $SpO_2$  and respiratory rate)
- Hypersensitivity monitoring
- Twelve-lead electrocardiogram (ECG)
- Severe Acute Respiratory Syndrome Coronavirus infection related signs and symptoms
- Radiography (chest x-ray and/or chest CT)
- Clinical laboratory test (clinical chemistry, hematology, and urinalysis)
- Physical examinations

[figure not shown]
### 3 Investigational Plan

#### 3.1 Study Design

This is a randomized, double-blind, placebo-controlled, parallel group, single ascending dose, Phase 1, pilot study to evaluate the safety, tolerability and virology of CT-P59 in combination with standard of care (SoC), except potential antiviral drugs and/or immune-based therapy under evaluation for treatment of SARS-CoV-2 infection, in patients with mild symptoms of SARS-CoV-2 infection. Approximately 18 patients in 3 cohorts are planned for enrollment and each cohort will consist of 6 patients, 5 of whom will receive CT-P59 and 1 of whom will receive a placebo. In each cohort, patients will be randomized in a 5:1 ratio to receive CT-P59 or placebo.

This study will be started with the lowest dose that will maximize safety and the dose levels will be escalated to the higher doses. The details of dose escalation and stopping criteria is specified in [Section 3.3](#). The overview of the study is presented in [Figure 3-1](#).

**Figure 3-1 Study Overview**

The study will be performed in a double-blind manner. To minimize the risk of unblinding, the study drug will be dispensed by unblinded study center personnel. The unblinded personnel who are responsible for dispensing study drugs will not be permitted to conduct any patient assessments.

#### 3.2 Rationale for Study Design

The design of this clinical trial follows the recommendation of the European Medicines Agency (EMA) Guideline on Strategies to identify and mitigate risks for first-in-human and early clinical trials with investigational medicinal product ([EMA, 2017](#)).

In line with the standard approach to early phase dose escalation study, the Sponsor is planning a pilot dose escalating Phase 1 study in patients with mild symptoms of SARS CoV-2 Infection to evaluate safety, tolerability and virology of CT-P59.

The dose escalation study has been designed to carefully assess the safety and tolerability of CT-P59 in patients with mild symptoms of SARS-CoV-2 infection, before progressing into the subsequent studies.

### **3.3 Dose Escalation and Stopping Criteria**

#### **3.3.1 Dose Escalation Criteria**

After each study drug administration, patients will be observed for 48 hours for evaluation of the safety and tolerability of the study drug. Despite the relatively long expected half-life of 18 days for CT-P59, the 48 hours of safety evaluation is justified given the expectation that any significant safety findings from the study drug administration should be apparent within post-48 hours considering the study drug is IV infusion.

When escalating dose from previous cohort to next cohort, Dose Escalation Committee (DEC) will review all available safety data of all patients in each cohort, within an observation period of 48 hours after study drug administration. If no safety or tolerability concern is observed, patients in next cohort will receive study drug.

Patients will be admitted for 72 hours post-study drug administration, and the duration of hospitalization may be extended at the discretion of the Investigator, so safety will be continuously monitored after the observation period of 48 hours.

If any safety concern including stopping rule specified in [Section 3.3.2](#) is raised, study can be temporarily stopped and the case will be immediate escalated to be reviewed at a DSMB meeting. The appointed independent DSMB members will evaluate the relationship to CT-P59 of the event with unblinded manner and review all available data and make a decision on continuation and the dose escalation of the study.

#### **3.3.2 Dose Stopping Rules**

The dose escalation from a previous cohort to the next cohort will be stopped if one or more of the following stopping criteria are met:

- Two or more patients in one cohort experience TEAEs of grade 3 or higher, which are considered to be related to study drug.

- Four or more patients in one cohort experience TEAEs of grade 2 or higher, which are considered to be related to study drug.
- One or more patients in one cohort experience a TESAE, which are considered to be related to study drug.

If an event corresponding to the above criteria occurs within the observation period of 48 hours in each cohort and the dosing is temporarily stopped under the decision of DEC, the appointed independent DSMB members will evaluate the relationship to CT-P59 of the event with unblinded manner and make a decision on continuation and the dose escalation of the study.

If an event corresponding to the above criteria occurs after observation period of 48 hours in the previous cohort occurrence, further progression to next cohort will be temporarily stopped and the appointed independent DSMB members will review data and make a decision on continuation and the dose escalation of the study.

If it was revealed that an event corresponding to the above criteria occurs and all the TEAEs are related to CT-P59 as reviewed by DSMB members, the study will be temporarily stopped. If it is decided to restart the trial and continue dose escalation based on further review of all available data, the supporting data will be submitted to the regulatory authority and agreed prior to trial restart.

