### **3.4.2 Treatment Period (Day 1 to prior to End-of-Treatment Visit)**

Inclusion and exclusion criteria will be re-confirmed on Day 1. If it is concluded that the patients are not eligible in Day 1 assessments, the patients will be considered as screening failure even if he/she was eligible based on assessments results performed during Screening Period.

Patients will be randomized in 5:1 ratio to receive CT-P59 or placebo once all eligibility criteria have been confirmed. Patients will receive a single dose of CT-P59 or placebo on Day 1.

All patients will be admitted to the study center on Day 1 and it is recommended to be confined up to Day 7. In-house stay period can be determined by Investigator considering the isolation regulation and/or public health capacity of the country, however all patients should be confined to the study center for at least 72 hours (until completion of all assessments on Day 3).

After discharge, the consecutive study visits will be carried out on an out-patient basis. During the isolation period according to the local regulation, patients will visit the study center using the transportation provided by Sponsor.

Patients will undergo the procedures at the time points specified in [Table 11-1](#) and [Table 11-2](#).

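### Read literally, Protocol 3.3.2 makes the study stop discretionary when one extra event is not CT-P59 related, even if criterion 1 or 2 is still met on CT-P59-related events

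*Protocol*

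**What the plan says.** Protocol 3.3.2 works in two layers.

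**Layer 1, escalation hold.** Escalation stops if any of three criteria is met:
1. "Two or more patients in one cohort experience TEAEs of grade 3 or higher, which are considered to be related to study drug"
2. "Four or more patients in one cohort experience TEAEs of grade 2 or higher, which are considered to be related to study drug"
3. at least one patient in the cohort has a TESAE related to study drug.

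Each cohort has 5 CT-P59 patients and 1 placebo patient (Protocol 3.1). The criteria refer to study drug, so the placebo patient counts. The DSMB then reviews causality unblinded and decides on continuation and escalation.

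**Layer 2, study stop.** The last paragraph of 3.3.2 makes a temporary stop of the study compulsory where "an event corresponding to the above criteria occurs and all the TEAEs are related to CT-P59 as reviewed by DSMB members". The next sentence says that, if a restart with further escalation is decided, "the supporting data will be submitted to the regulatory authority and agreed prior to trial restart". The synopsis and SAP 4.1 repeat the layer 2 condition and attach the regulatory submission directly to the compulsory stop.

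**Outside these layers.** Under Protocol 3.3.1, on any safety concern the "study can be temporarily stopped and the case will be immediate escalated to be reviewed at a DSMB meeting". That stop is optional.

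Protocol 3.3.1, 3.3.2, 9.4.1 and 9.4.2 do not say what follows when some flagged events are not upheld as CT-P59 related but the upheld ones still reach a threshold. Section 9.4.2 leaves further detail to a DSMB charter, which is not among the documents.

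**The concern.** Criteria 1 and 2 are counts, while layer 2 adds a requirement that every event be CT-P59 related. Joined together, they let an additional event weaken the rule. Two CT-P59 patients with confirmed related grade 3 events compel a stop. Add a related-looking grade 3 event on placebo, or a third CT-P59 event that the DSMB overrules, and the stop is no longer compelled. The evidence against CT-P59 is unchanged.

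Such reversals are plausible. The possible category in Protocol 6.1.1.3 includes events that other factors could explain, and SAP 12.1 counts possible as related. The patients are symptomatic, and Protocol 6.1.13 lets investigators report infection signs as AEs at their discretion (diary symptoms are not so reported, Protocol 6.3.1).

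What is at stake is the automatic stop and, at least in the synopsis and SAP wording, the regulatory step. "Patients will receive a single dose of CT-P59 or placebo on Day 1" (Protocol 3.4.2), so the exposure concerned is that of patients not yet dosed. Expedited reporting under Protocol 6.1.1.1.7 covers serious events. It does not cover criteria 1 and 2 when non-serious events meet them. An outside check has value here because the human data required before this study starts are "Safety data from cohort 1 and 2 (10 mg/kg, 20 mg/kg respectively) up to Day 7 in Study CT-P59 1.1" (Protocol 1.3.2), while cohorts 2 and 3 receive 40 and 80 mg/kg (Protocol 5.2).

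**Working it through.** The documents give no operating characteristics for this rule, so there is no figure to reproduce. The check has two parts.

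**1. Logic.** For one cohort, let a be the CT-P59 patients with a DSMB-confirmed related event, u the CT-P59 patients flagged under blind but overruled, and b = 1 if the placebo patient is flagged (otherwise 0). Take the phrase to mean all events of the relevant grade that were flagged as related. The literal stop needs u = 0 and b = 0.

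- Criterion 1 (a ≥ 2): the (a, u) pairs number 4 + 3 + 2 + 1 = 10, times 2 for placebo = 20 patterns. The literal stop is compulsory in 4 (a = 2, 3, 4, 5).
- Criterion 2 (a ≥ 4): (2 + 1) × 2 = 6 patterns. The literal stop is compulsory in 2.

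A recount on confirmed CT-P59 events would compel the stop in all 20 and all 6. The patterns are not equally likely, so these ratios are not probabilities.

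**2. Probability.** All rates are assumptions. Let p be the chance that a CT-P59 patient is flagged, q the chance that the placebo patient is flagged, and r the chance that the DSMB overrules a CT-P59 flag. Then X ~ Bin(5, p) is the number flagged and Y ~ Bin(5, p(1−r)) the number confirmed, with one flag per patient. The threshold is m = 2 for criterion 1 and m = 4 for criterion 2.

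P(criterion met, stop not compulsory) = P(Y ≥ m) − (1−q) × Σ over x ≥ m of P(X = x)(1−r)^x

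With r = 0 this reduces to q × P(X ≥ m).

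*Placebo event only, m = 2, p = q = 10%:* P(X ≥ 2) = 1 − 0.59049 − 0.32805 = 0.08146; × 0.10 = 0.00815.

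*Both routes, m = 2, p = 20%, q = r = 10%:* P(Y ≥ 2) = 0.22235 and the sum is 0.20760; 0.22235 − 0.9 × 0.20760 = 0.0355.

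| Criterion | p | q | r | Met on confirmed CT-P59 events | Met, stop not compulsory | Share |
|---|---|---|---|---|---|---|
| 1 | 5% | 5% | 0 | 0.02259 | 0.00113 | 5% |
| 1 | 10% | 10% | 0 | 0.08146 | 0.00815 | 10% |
| 1 | 20% | 10% | 0 | 0.26272 | 0.02627 | 10% |
| 1 | 5% | 0 | 10% | 0.01849 | 0.00028 | 1.5% |
| 1 | 20% | 0 | 10% | 0.22235 | 0.01475 | 6.6% |
| 1 | 20% | 10% | 10% | 0.22235 | 0.0355 | 16% |
| 2 | 20% | 10% | 0 | 0.00672 | 0.00067 | 10% |
| 2 | 40% | 10% | 0 | 0.08704 | 0.00870 | 10% |
| 2 | 20% | 0 | 10% | 0.00449 | 0.00010 | 2.3% |

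These are illustrations, not bounds. At p = q = 2% and r = 0, criterion 1 gives 0.008%. In a stress case with half the CT-P59 patients flagged, 20% overruled and q = 10%, the share is 41% for criterion 1 (0.663 × 0.411 = 0.27 per cohort) and 23% for criterion 2.

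Criterion 3 is left out. One CT-P59-related TESAE is a qualifying event by itself, so it is unclear which events the phrase then covers.

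**The case against.** **The phrase may mean only the events that matter.** The paragraph follows two others in which the DSMB assesses the relationship to CT-P59 unblinded. Read by its purpose, it asks whether the criterion survives unblinding, and the loss is then zero. Nothing suggests that a DSMB holding two confirmed grade 3 events would treat a placebo event as a reason not to stop. This narrows the point without removing it. The text does not state that reading. Taking the phrase as the events behind the blinded trigger does not help once flagged patients exceed the threshold.

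**The charter may require a recount.** It may. If so, only the protocol wording is at issue.

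**Regulatory agreement may not be lost.** A reader might infer that it always lapses. The documents do not support that. In 3.3.2 the restart sentence stands apart with its own condition and could also cover a discretionary stop. Only the synopsis and SAP tie the step clearly to the compulsory stop.

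**Patients remain protected.** A reader might also infer that dosing would continue unchecked. It would not. The escalation hold is mandatory, the DSMB decides unblinded, and the stop in 3.3.1 is available. If the healthy-subject study raises a concern, "the DSMB will be required not to proceed with the dosing of the next cohort in the patient study" (Protocol 1.3.2). Urgent safety measures require immediate written notice to the licensing authority (Protocol 1.4). All of this stands.

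**Some grade 3 events are also serious.** CTCAE grade 3 includes indicated prolongation of hospitalization (Protocol 6.1.1.2), prolongation makes an event serious (6.1.1.1.1), and patients are confined for at least 72 hours (3.4.2). Such events also engage criterion 3 and expedited reporting. The criterion 1 figures do not separate them, so they overstate the cases without that backup.

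**Conclusion.** The point holds as a wording defect. Followed literally, layer 2 can make the study stop discretionary while criterion 1 or 2 is still met on DSMB-confirmed CT-P59-related events.

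For criterion 1, the assumed cases that allow a placebo event give about 0.1% to 3.6% per cohort (p 5% to 20%, q 5% to 10%, overruling 0 or 10%). Overruling alone at p = 5% gives 0.03%. Once the criterion is met, and with no overruling, the share of stops affected equals the placebo flag rate. The size rests wholly on assumed rates and on the literal reading.

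Two stronger readings should be resisted. The 16 of 20 patterns in which the literal stop fails do not mean that it usually fails, because most of those patterns are unlikely. Nor is counting the placebo patient in layer 1 a fault: that layer is only a precautionary hold under blind. No claim is made that criterion 3 fails, since its wording is ambiguous.

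With the hold and the unblinded DSMB decision intact, this is a change to consider.

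**What to change.** In Protocol 3.3.2 and the synopsis, replace the layer 2 condition with:

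> *If, after unblinded DSMB review, one or more of the above criteria are met counting only CT-P59-treated patients with events judged related to CT-P59, the study will be temporarily stopped.*

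Keep the thresholds and the regulatory sentence. Align SAP 4.1, and check that the DSMB charter agrees.

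State openly that this also settles criterion 3: one DSMB-confirmed CT-P59-related TESAE triggers the stop whatever other TESAEs occur.

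No existing compulsory stop is lost, because whenever every flagged event is CT-P59 related the recount equals the blinded count. A criterion reached only by counting the placebo patient still does not compel a stop.

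The cost is one sentence in two places of the protocol, a matching SAP edit and a charter check. Thresholds, sample size and data collection do not change. The downside is that the compulsory stop may apply slightly more often under all three criteria. For criterion 1, the increase over the literal rule is the stop-not-compulsory column of the table. For criterion 3 it is not quantified.
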